Any initially HIV-negative participant with a positive HIV test of any type during the course of the study will be instructed to come in immediately for an HIV+ (Seroconversion) visit. Patients seroconverting while on PrEP will be offered the choice to either (1) intensify to an approved 3 or 4 drug antiretroviral regimen for presumptive HIV treatment, as prescribed by an expert HIV clinician, or (2) stop taking PrEP. At the HIV+ (seroconversion) visit, the participant will have blood drawn for confirmatory HIV Western blot and quantitative HIV RNA PCR with reflex to HIV-1 genotype, as well as DBS testing for drug levels. Additional blood specimens will be sent to the UCSF laboratory of [name], for an allele-specific PCR-based assay for detection of minor variant drug resistance at FTC/TDF-selection codons. (See Appendix S.) Women of reproductive potential will have a rapid urine pregnancy test. A medical history, physical exam, risk assessment, risk reduction counseling, adherence assessment, and STI evaluation will be performed. The participant will be asked to return within one week to receive the results of the confirmatory HIV testing. For those confirmed to be HIV infected, EBAC/DYC will provide counseling and immediate linkage to HIV primary care according to usual clinic practice. HIV infected participants who had elected intensification to highly active antiretroviral therapy (HAART) will be encouraged to continue their treatment regimen until HIV primary care is established. Those confirmed to be HIV uninfected will not resume the study protocol, and, if they have elected intensification to HAART, will discontinue treatment. Some patients who prove to be HIV uninfected

may choose to restart PrEP outside this protocol, with monitoring as appropriate for the clinical circumstances under the guidance of an expert HIV clinician.

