Any participant with signs and symptoms at any study visit suggestive of acute retroviral syndrome, in the setting of recent high risk behavior, but without serologic evidence of HIV infection to date, will have qualitative HIV RNA testing sent and will be offered immediate intensification to an approved 3 or 4 drug highly active antiretroviral therapy (HAART) regimen as prescribed by an expert HIV clinician. This regimen will be continued, with clinically appropriate monitoring, until results of RNA testing are obtained. If HIV RNA testing is negative, the patient will discontinue the intensification agent(s), and will be offered continued Truvada® prophylaxis, as scheduled on the PrEP protocol. If HIV RNA testing is positive, the patient will be instructed to continue HAART, and will be brought in for an HIV+ (Seroconversion) visit as above. EBAC/DYC will provide counseling and immediate linkage to HIV primary care according to usual clinic practice.

IX.4 Pregnancy

Women who become pregnant during the study may continue PrEP, particularly since risk of HIV acquisition may be higher during this period. The clinician will disclose to pregnant women and those planning pregnancy that safety for infants exposed to Truvada® during pregnancy is not fully assessed, but that no harm has been reported. Pregnant participants will be offered the options of continuing or stopping PrEP, and in all cases will be referred immediately for prenatal care. Upon discontinuation of PrEP during pregnancy, the clinician will inform prenatal care providers of TDF/FTC use in early pregnancy and will coordinate care to maintain HIV prevention during pregnancy. Participant information will be submitted to the FDA's Antiretroviral Pregnancy Registry. Women who give birth will be counseled not to breastfeed, in accordance with US guidelines. PrEP will be discontinued for any woman who intends to breastfeed.

IX..5 Social harms

Participation in the study could lead to social harms that may include loss of privacy, stigmatization, interference with employment, and coercion. Participants who report social harms will be referred to a clinician. PrEP may or may not be continued depending upon the preference of the patient and the judgment of the clinician. Social harms leading to discontinuation of study drug will be recorded on an Adverse Event form and reported to CHRP and Gilead Sciences.

X. Data collection and storage

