Appendix 12: Procedures for nucleic acid (NAT) testing for infection with HIV, HCV, and HBV

- CRUSH staff will collect blood at all visits from HIV-negative participants not receiving PrEP for HIV/HCV/HBV NAT testing.
- Each blood sample will be labeled using a unique, de-identified, five-digit number barcoded sticker provided by the Red Cross. Participants will also be given this 5-digit number so that they may retrieve their HIV test results (if negative) via the web or interactive voice response system two weeks after their test date.
- Samples will be sent in batches directly to the American Red Cross reference laboratory in St. Louis, MO for NAT testing three times a week, and CRUSH staff will notify the University of California, San Diego Antiviral Research Center (AVRC) staff via a secure web form that a NAT test was performed (only 5-digit code and test date entered).
- After the Red Cross completes NAT testing (usually within 5 days), the Red Cross will send the encrypted results electronically to the UCSD Center for AIDS Research (CFAR) Bioinformatics and Information Technologies (BIT) Core via secure FTP.
- Upon receiving the results from the Red Cross, the UCSD BIT Core will automatically decrypt the results and import them into a secure database located on servers hosted at the UCSD San Diego Supercomputing Center (SDSC) and Antiviral Research Center (AVRC).
- The decrypted results will be matched up to the 5-digit code provided by CRUSH staff to the AVRC via the above-mentioned web form. This matching allows the BIT Core to monitor the flow of data closely should any reporting fail between Oakland, the Red Cross and the AVRC.
- In cases of negative HIV NAT results, participants can obtain their results two weeks after testing via web or interactive voice response using their 5-digit code, at theearlytest.ucsd.edu
- For HIV positive results, AVRC staff and CRUSH staff will be automatically notified via email (including only 5-digit code, test date, and positive result) by BIT Core scripts. This allows

sufficient time for clinical staff to directly contact positive individuals before the two-week negative results access window opens.

- HCV and HBV negative results are not made available to participants through the web or interactive voice response, but positive results will be reported via email to AVRC and CRUSH staff so that they may directly contact participants.

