Appendix 13: Allele-specific PCR-based minor variant drug resistance assay

The development of drug-resistant virus in individuals who become infected while taking PrEP is a concern that warrants close monitoring. While the detection of FTC-TDF selected drug resistance in clinical trial participants who fail PrEP is rarely seen using conventional genotyping and ultrasensitive assays, continued study and monitoring is needed as FTC-TDF PrEP use is expanded to non-research settings. Ongoing and planned demonstration projects present an ideal opportunity to monitor the incidence and nature of drug resistance selected by PrEP.

HIV-1 drug resistance testing for the CRUSH PrEP demonstration project will be performed at UCSF's AIDS Research Institute Laboratory of Clinical Virology (ARI-UCSF LCV) using specimens collected from HIV infected participants at first evidence of infection. HIV-1 genotypic resistance testing will be performed by bulk sequencing of the protease and reverse transcriptase region using the FDA-cleared TRUGENE genotyping kit under clinical protocols. Individual drug resistance mutations and drug susceptibility interpretations are reported. For increased sensitivity, a validated allele-specific PCR-based minor variant drug resistance assay will be performed for detection of minor variant drug resistance at FTC/TDF-selection codons K65R, K70E, and M184V/I that may be present at a low level, and not detected by the sequence-based assay. The % drug resistance codon above the biologic cutoff (BCO) at each drug resistance site is reported.

A single specimen is used for both assays. Specimens of at least 1.0 mL blood plasma will be obtained from participants, spun, and frozen, then sent to [name] lab, with no identifying information except for a unique identifier code number. A minimum HIV-1 viral load of 500 copies/mL by standard commercial assays is required. Results will be reported back to CRUSH staff by code number.

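### On the suspected-acute-HIV pathway, PrEP participants who accept immediate HAART have their resistance specimen specified only after drugs have been added

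*Protocol*

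**What the plan says.** Protocol section IX.3 describes two routes to a diagnosis of HIV during the study.

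- **A positive HIV test of any type.** The participant "will be instructed to come in immediately for an HIV+ (Seroconversion) visit". Blood at that visit is for a confirmatory Western blot and "quantitative HIV RNA PCR with reflex to HIV-1 genotype, as well as DBS testing for drug levels". Further blood goes to the UCSF laboratory for the allele-specific minor-variant assay. A participant on PrEP is offered either intensification or stopping.
- **Suspected acute infection with no serologic evidence.** The participant "will have qualitative HIV RNA testing sent and will be offered immediate intensification to an approved 3 or 4 drug highly active antiretroviral therapy". The added drugs continue until the RNA result is known. After that, "If HIV RNA testing is positive, the patient will be instructed to continue HAART, and will be brought in for an HIV+ (Seroconversion) visit".

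The visit schedule (Appendix 4) agrees. As the table reads, quantitative RNA and genotype are marked only in the HIV Ab+ column. The risk-guided RNA test at week 4, at weeks 12 to 48 and at the stop-drug visit is qualitative.

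Appendix 13 says resistance testing uses "specimens collected from HIV infected participants at first evidence of infection". It adds that "A single specimen is used for both assays", asks for at least 1.0 mL of plasma, spun and frozen, and sets a minimum load of 500 copies/mL. Its stated purpose is to track how often, and in what form, PrEP selects resistant virus.

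**The concern.** On the second route, a participant who accepts treatment has the resistance specimen taken after new agents have been started, although blood was drawn for RNA before they started. Two things are at stake.

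1. **What the specimen shows.** Blood drawn before the extra agents reflects virus under FTC/TDF alone, which is what Appendix 13 sets out to monitor. Later blood reflects FTC/TDF plus the added drugs.
2. **Whether the assays can be run.** The added drugs are meant to lower the viral load, and Appendix 13 needs 500 copies/mL. A specimen from before the added drugs cannot be obtained afterwards unless plasma was kept.

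Few participants are likely to become infected on PrEP, so each specimen carries weight for this monitoring.

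**Working it through.** **Step 1: order of events for a participant who accepts HAART**

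| Step | Provision | Virological blood specified | Drugs at the time of the draw |
|---|---|---|---|
| Symptomatic visit | IX.3, suspected acute infection | Qualitative RNA | FTC/TDF |
| Wait for the result | IX.3 | None named | FTC/TDF plus added agents |
| HIV+ visit | IX.3 and Appendix 4 | Quantitative RNA, genotype, minor-variant blood | FTC/TDF plus added agents |

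The resistance draw therefore falls after intensification. A participant who declines HAART is not affected. Nor is one found by a positive antibody test, who is called in and can be sampled before any drug is added.

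**Step 2: does another provision supply an earlier specimen?** Appendix 13 gives the timing in general terms but orders no draw at the symptomatic visit. Section VII.3 sends NAT blood from all HIV-negative participants at every visit, while Appendix 12 narrows this: "CRUSH staff will collect blood at all visits from HIV-negative participants not receiving PrEP". On either reading those samples go to the Red Cross laboratory, and no retention for resistance testing is described. The documents do not mention keeping plasma from the qualitative RNA draw.

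**Step 3: the 500 copies/mL minimum (illustration only).** The documents give no turnaround for this RNA test, no starting load and no rate of fall on treatment. The nearest laboratory time is in Appendix 12: "After the Red Cross completes NAT testing (usually within 5 days". That is an analogue, since Appendix 12 describes testing for people not on PrEP.

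Assume a fall of r = 0.1 to 0.3 log10 copies/mL per day (a half-life of about 3 days to 1 day). The load on day t is V0 × 10^(−r·t), so the specimen is below the minimum when V0 < 500 × 10^(r·t).

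- t = 5, r = 0.1: 500 × 10^0.5 = 1,581.
- t = 5, r = 0.3: 500 × 10^1.5 = 15,811.
- t = 7, r = 0.1: 500 × 10^0.7 = 2,506.
- t = 7, r = 0.3: 500 × 10^2.1 = 62,946.

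The rate needed to reach 500 is log10(V0/500)/t.

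- V0 = 10,000: 1.301/5 = 0.26 per day, or 1.301/7 = 0.19 per day. Both lie inside the assumed range.
- V0 = 100,000: 2.301/5 = 0.46 per day, or 2.301/7 = 0.33 per day. Both lie outside it.

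At delays of 5 to 7 days, low and moderate starting loads could fall under the minimum. A load of 100,000 would not.

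**Step 4: how many people.** Appendix 1 projects 135 HIV-negative participants interested in PrEP, before the clinical exclusions in VII.5 and VII.6. The documents give no incidence. At an assumed 1 to 5 infections per 100 over the project, that is 135 × 0.01 = 1.35 to 135 × 0.05 = 6.75, or about 1 to 7 people. The documents offer no basis for the share who would enter this pathway or the share who would fall below 500, so I do not go on to a count of lost results.

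**The case against.** The case on the other side is substantial and narrows the point in four ways.

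- **Conflict with Appendix 13.** A reader might infer that IX.3 contradicts the appendix. That depends on what counts as first evidence of infection. The most natural reading is the draw that proved RNA-positive. It can also mean the date of the result, since nobody is known to be infected before then, and on that reading the texts agree. On either reading, the resistance blood is drawn after drugs have been added.
- **A lost pre-treatment sample.** A reader might call the earlier specimen pre-treatment. It is not, because these participants are prescribed daily FTC/TDF and IX.3 itself speaks of intensification. The codons in Appendix 13 are those selected by FTC/TDF, and both specimens follow exposure to it. The documents do not show that a few days of added agents would change what the assays find. The earlier specimen is cleaner, but the load minimum is the more concrete harm.
- **Loss of both results.** A reader might infer that a load under 500 always costs both assays. IX.3 orders a reflex genotype and, separately, further blood for the minor-variant assay, and it states no minimum for the genotype. Both are lost only if Appendix 13's single specimen is what is used.
- **Importance.** Resistance is not among the three aims, and the SAP names no resistance endpoint or analysis. An expert clinician prescribes the regimen with suitable monitoring and might take baseline blood anyway. The protocol leaves room for that but does not require it, and routine care cannot be assumed to supply a specimen for a study assay at a named laboratory.

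What stands is the order of steps and the absence of any instruction to keep the earlier plasma.

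**Conclusion.** The point holds in a narrow form. For a PrEP participant with suspected acute HIV and negative serology who accepts immediate HAART, the plan specifies resistance sampling only after intensification has begun, although blood is already drawn beforehand. This is a poorer specimen for the monitoring described in Appendix 13, and it may be below 500 copies/mL.

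The frequency cannot be estimated from the documents. Loss is probably uncommon, because it needs a symptomatic, antibody-negative, RNA-positive participant who accepts HAART and whose load then falls under the minimum. The thresholds above rest on assumed rates of fall and on a delay borrowed from a different test. They show that loss is possible, not how likely it is.

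Severity is minor. No stated aim and no SAP endpoint depends on the result. The change is worth making because it is cheap and a missed specimen cannot be recovered.

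**What to change.** Add one instruction to the suspected-acute-infection paragraph of IX.3. Before the first intensified dose, the draw that supplies the qualitative RNA should also yield plasma, spun and frozen as in Appendix 13. The volume should be at least 1.0 mL for the two resistance assays, plus enough for quantitative RNA, because Appendix 13 does not say that 1.0 mL covers all three. If the RNA is positive, run quantitative RNA, genotype and the minor-variant assay on that specimen. If it is negative, discard it. A matching note on the risk-guided RNA row of Appendix 4 would keep the schedule consistent.

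The cost is one extra stored aliquot per suspected case. There is no new visit and no new assay, and HAART need not be delayed.

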7. Arnold, E. *et al. Understanding the feasibility and acceptability of implementing Pre-Exposure Prophylaxis (PrEP) to prevent HIV among African American men who have sex with men and transgender people in Northern California: Final Progress Report.* (UCSF Center for AIDS Prevention Studies: San Francisco, CA, 2011).
8. California Department of Public Health Sexually Transmitted Diseases (STD) Control Branch in collaboration with the California STD/HIV Prevention Training Center A Clinician's Guide to Sexual History Taking. (2011).
10. Giordano, T. P. *et al.* Measuring adherence to antiretroviral therapy in a diverse population using a visual analogue scale. *HIV clinical trials* **5**, (2004).
11. APHA: Adherence to HIV Treatment Regimens. at
[<http://www.apha.org/programs/resources/HIV+-+AIDS/reshivregimens.htm>](http://www.apha.org/programs/resources/HIV+-+AIDS/reshivregimens.htm)

Appendix 1

CRUSH Study Enrollment Projection

Study Enrollment for the CRUSH Project

Assumes annual test volumes as follows:
La Clinica de la Raza 150
HYFY 25
Berkeley Builds Capacity 25
Asian Health 150
HEPPAC 85
RYSE 40
[name]/Oakland Pride 150
Social network testing 50
Also assumes that enrollment starts 3 months after study start and ends 12 months prior to study end for 2.75 years of enrollment

Total New HIV tests
N= 1857
Social network testing= 138
Community partners= 1719

Assuming a positivity of 2.5% for community testing and 10% for social network testing, and an unchanged rate of newly referred positive clients from other agencies (48 per year)

Newly referred HIV positives
189

HIV positive clients already engaged at DYC who choose to enroll N=100

Newly referred HIV negatives N= 1800

Assumes that two thirds of positives and a quarter of negatives are both linked to CRUSH and willing to participate in study data collection , and that 30% of negatives will be interested in PrEP

Total number of HIV positives enrolled in CRUSH
N=225

HIV negative clients enrolled
N=450

HIV negative and not interested in PrEP
N=315

HIV negative and interested in PrEP
N=135

September 2013

Updated December 17, 2013

Appendix 4:

Study Visit Schedule

Study Visit Schedule (

Week	Screening*	0	4	12, 24, 36, 48		Stop drug	HIV Ab+
Clinical Assessments/Interventions							
Screen inclusion/exclusion criteria	x						
Obtain informed consent	x						
Medical history and focused review of systems	x	x	x	x		x	x
STI Risk Assessment	x	x	x	x		x	x
Adherence Assessment			x	x		x	x
Targeted Physical Exam	x	x	x	x		x	x
Adherence counseling		x	x	x		x	x
Risk reduction counseling, condom distribution	x	x	x	x		x	x
Drug dispensing		x	x	x			
ACASI (weeks 0, 4, 24, 48 only)		x	x	x			
Laboratory Assessments							
Creatinine	x		x	x			
Urine dipstick protein	x	x	x	x			
Rapid urine pregnancy test (if relevant)	x	x	x	x		x	x
HBsAg (and HBsAb if not documented)	x						
ALT/AST (if HBsAg+)		x	x	x		x	x
HBV DNA + LFTs(if HBsAg+)		x	x	x		x	x
Serum HIV Ab EIA	x					x	
Rapid Oral HIV Ab	x	x	x	x		x	
HIV Ab Western Blot							x
HIV RNA Qualitative PCR	x						
HIV RNA Qualitative PCR (risk-guided)			x	x		x	
HIV RNA Quantitative PCR							x
HIV-1 genotype							x
STI laboratory evaluation	x			x		x	x
DBS Drug Level Testing			x	x		x	x
*-4 to -1 weeks September 2013						Page 40 of 53	

Appendix 5:

DRAFT

ACASI Behavioral

Questionnaire

Appendix 6:

Maslach Burnout Inventory (MBI)

Appendix 7: Non-serious Adverse Events & Side Effects Inventory

Non-serious Adverse Events & Side Effects Inventory

3 Other Action Taken

¹Severity

1=Mild
2=Moderate
3=Severe
4=Life-Threatening

²Action taken with Study Drug

1=Not changed
2=Interrupted
3=Withdrawn

1 = None
2 = Medication
Required*
3 =
Hospitalization/Prolonged Hospitalization
4 = Other Treatment Required

*Any medication taken for an AE should be recorded on the Concomitant Medication Log

Appendix 8:

Serious Adverse Event Report Form

SERIOUS ADVERSE EVENT REPORT FORM

For the purposes of this form, a serious adverse event is any untoward medical occurrence that results in death, is life-threatening, requires or prolongs hospitalization, causes persistent or significant disability/incapacity, results in congenital anomalies/birth defects, or in the opinion of the investigators represents other significant hazards or potentially serious harm to research subjects or others. A serious adverse event is considered unexpected if it is not described in the Package Insert or in the Investigator's Brochure (for FDA investigational agents), in the protocol, or in the informed consent document.

INSTRUCTIONS:

Please complete the information requested below and forward a copy to the IRB and the sponsor as soon as possible, but not later than seven (7) days in the case of death or life-threatening serious adverse events or within fifteen (15) days after the occurrence of all other forms of serious adverse events. In addition, continue to follow FDA and the NIH Office of Biotechnology Activities (OBA) reporting requirements if your research involves an IND/IDE or gene transfer.

PROTOCOL #: _____ - _____	PROTOCOL TITLE: Connecting Resources for Urban Sexual Health:	
PRINCIPAL INVESTIGATOR: [name].	East Bay AIDS Center Fax:	Office Phone: E-mail:
DATE OF SERIOUS ADVERSE EVENT:	____ / ____ / ____	
SUBJECT ID:		
WAS THIS AN UNEXPECTED ADVERSE EVENT?	Yes [] No []	
BRIEF DESCRIPTION OF SUBJECT(S) (Do NOT include identifiers.)	SEX: M/F AGE: _____ Event:	
BRIEF DESCRIPTION OF THE NATURE OF THE SERIOUS ADVERSE EVENT:		

CATEGORY (outcome) OF THE SERIOUS ADVERSE EVENT:  death  disability/incapacity  life-threatening  congenital anomaly/birth defect  hospitalization-initial or prolonged  required intervention to prevent permanent impairment  other	RELATIONSHIP OF SERIOUS ADVERSE EVENT TO RESEARCH:  1 = unrelated (clearly not related to the research)  2 = unlikely (doubtfully related to the research)  3 = possible (may be related to the research)  4 = probable (likely related to the research)  5 = definite (clearly related to the research)
What steps do you plan to take as a result of the adverse event reported above?	 no action required  continue study drug  discontinue study drug  other, describe:
REPORTER'S SIGNATURE:	DATE:
INVESTIGATOR'S SIGNATURE:	DATE:

Appendix 9: PrEP Informational Fact Sheets for Participant

Appendix 10:

Integrated Next Step

Counseling Assessment Tool

Appendix 11: Monitoring of hepatitis B surface antigen (HBsAg) positive participants on Truvada® PrEP:

- Check both HBsAg and HBsAb on screening visit.
- If HBsAg negative and HBsAb negative, immunize with HBV series (3 injections over 6 months). Recheck HBsAb at week 48 if immunized.
- If HBsAg positive, check at baseline: AST/ALT, total bilirubin, alkaline phosphatase, prothrombin time, albumin, hepatitis B DNA quantitative PCR, and hepatitis BeAg. Perform a clinical evaluation for stigmata of cirrhosis.
- For all HBsAg positive participants, Hepatitis A total antibody and if immunize (2 vaccines 6 months apart) if seronegative.
- For all HBsAg positive participants regardless of HBeAg status, counsel participant regarding risk of HBV flare on PrEP; monitor HBV DNA quantitative PCR and ALT/AST at 3, 6 and 12 months on PrEP, and then 6 months after stopping PrEP.
- If HBeAg positive at baseline, recheck HBeAg at 3, 6 and 12 months of PrEP, or until HBeAg turns negative.
- Flares in ALT/AST, or evidence of virologic breakthrough by HBV DNA, will be managed per standard clinical protocols according to AASLD guidelines.

